7.0 EFFICACY ASSESSMENT

7.1 Efficacy Variables

Tumor response and/or disease progression will be assessed by a CT scan (or other appropriate modalities such as by way of MRI consistent with the modality used prior to treatment) utilizing RECIST v1.1 criteria. Assessments will be performed within 3 weeks before screening every 8 weeks thereafter, and at the final visit, if not performed within the last four weeks. If subjects respond to treatment and are able to have their disease resected, the patient's response will be assessed prior to the surgery. The primary *clinical efficacy* endpoint is PFS_{8 weeks} as determined by RECIST v1.1 criteria. Analyses of these endpoints are described in Section 13.

7.2 RECIST v1.1 Criteria for Tumor Response

Changes in the measurable lesions over the course of therapy will be evaluated using the RECIST v1.1 criteria.

7.2.1 Definition of Lesions

7.2.1.1 Measurable Disease

The presence of at least one measurable lesion. If the measurable disease is restricted to a solitary lesion, its neoplastic nature should be confirmed by cytology/histology.

7.2.1.2 Measurable Lesions

Lesions that can be accurately measured in at least one dimension with longest diameter ≥ 20 mm using conventional techniques or ≥ 10 mm with CT scan.

7.2.1.3 Non-measurable Lesions

All other lesions, including small lesions (longest diameter < 20 mm with conventional techniques or < 10 mm with a CT scan), bone lesions, leptomeningeal disease, ascites, pleural/pericardial effusion, inflammatory breast disease, lymphangitis cutis/pulmonis, cystic lesions and also abdominal masses that are suspicious though may or may not be confirmed and followed by imaging techniques.

All measurements should be taken and recorded in metric notation, using a ruler or calipers. All baseline evaluations should be performed as closely as possible to the beginning of treatment and never more than 14 days before the beginning of the treatment. The same method of assessment and the same technique should be used to characterize each identified and reported lesion at baseline and during follow-up. Clinical lesions will only be considered measurable when they are superficial (e.g., skin nodules and palpable lymph nodes). For the case of skin lesions, documentation by color photography including a ruler to estimate the size of the lesion is required.

7.2.2 Methods of Measurement

CT and MRI are the best currently available and reproducible methods to measure target lesions selected for response assessment. Conventional CT and MRI should be performed with cuts of 10 mm or less in slice thickness contiguously. Spiral CT should be performed using a 5 mm contiguous reconstruction algorithm. This applies to tumors of the chest, abdomen and pelvis. For accurate objective response evaluation, ultrasound should not be used to measure tumor lesions. However, ultrasound is a possible alternative to clinical measurements of superficial palpable lymph nodes, subcutaneous lesions and thyroid nodules. Ultrasound might also be useful to confirm the complete disappearance of superficial lesions usually assessed by clinical examination. Cytology and histology can be used to differentiate between PR and CR in rare cases (e.g., after treatment to differentiate between residual benign lesions and residual malignant lesions in tumor types such as germ cell tumors).

7.2.3 Baseline Documentation of "Target" and "Non-Target" Lesions

All measurable lesions up to a maximum of 2 lesions per organ and 5 lesions in total, representative of all involved organs should be identified as target lesions and recorded and measured at baseline. Target lesions should be selected on the basis of their size (lesions with the longest diameter) and their suitability for accurate repeated measurements (either by imaging techniques or clinically). A sum of the longest diameter (LD) for all target lesions will be calculated and reported as the baseline sum LD. The baseline sum LD will be used as reference by which to characterize the objective tumor response. All other lesions (or sites of disease) should be identified as non-target lesions and should also be recorded at baseline. Measurements of these lesions are not required, but the presence or absence of each should be noted throughout follow-up.

7.2.4 Definitions of Tumor Response-Measurable Disease

7.2.4.1 Complete Response (CR)

The disappearance of all known disease, determined by two observations not less than 4 weeks apart. There can be no appearance of new lesions.

7.2.4.2 Partial Response (PR)

A 30% or more decrease in the sum of the LD of target lesions that have been measured to determine the effect of therapy by two observations not less than 4 weeks apart. There can be no appearance of new lesions or progression of any lesion.

7.2.4.3 Progressive Disease (PD)

At least a 20% increase in the sum of the LD of target lesions, taking as reference the smallest sum LD recorded since the treatment started, the appearance of one or more new lesions and/or an unequivocal progression of non-target lesions.

7.2.4.4 Stable Disease (SD)

Neither sufficient shrinkage to qualify for PR nor sufficient increase to qualify for PD, taking as reference the smallest sum LD since the treatment started.

7.3 Evaluation of Best Overall Response

The best overall response is the best response recorded from the start of the treatment until disease progression/recurrence (taking as reference for progressive disease the smallest measurements recorded since the treatment started). The patient's best response assignment will depend on the achievement of both measurement and confirmation criteria.

Table 12. Response Evaluation. Note: If subjects respond to treatment and are able to have their disease resected, the patient's response will be assessed prior to the surgery.

Target Lesions	Non-Target Lesions	New Lesions	Overall Response	Best Response for this Category Also Requires:
CR	CR	No	CR	>4 wks. confirmation
CR	Non-CR/Non-PD	No	PR	>4 wks. confirmation
PR	Non-PD	No	PR	
SD	Non-PD	No	SD	Documented at least once >4 wks. from baseline
PD	Any	Yes or No	PD	no prior SD, PR or CR
Any	PD*	Yes or No	PD	
Any	Any	Yes	PD	

* In exceptional circumstances, unequivocal progression in non-target lesions may be accepted as disease progression.

Note: Patients with a global deterioration of health status requiring discontinuation of treatment without objective evidence of disease progression at that time should be reported as "symptomatic deterioration". Every effort should be made to document the objective progression even after discontinuation of treatment.

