
	
Trial Auditing
 
The multi-institutional coordinator will arrange all primary source documents for the patients to be audited. This will include collecting copies of the primary source data for any patients treated at other sites.

Statistical Design, Feasibility, and Trial Duration
	
This is a multi-institutional single arm, open label Phase I/II study to evaluate the PFS_{8weeks} of the combination of LEE-011 plus everolimus, in patients with metastatic pancreatic cancer refractory to 5-fluorouracil (5-FU) and gemcitabine-based chemotherapy. Previous studies of third-line therapy in mPAC are limited but reveal stable disease in 25-31% of patients with no partial or complete responses (31% of patients in the GVAX/CRS-207 combination vaccine study had stable disease but only 52% of these patients were treated in the third-line setting)^(5, 6). It is hoped that the combination of LEE-011 plus everolimus can increase the PFS_{8weeks} to at least 50%, though early stopping rules are in place for lack of efficacy.
 
All patients meeting the eligibility criteria and who have signed a consent form, have begun treatment, are not lost to follow-up, and are not taken off study for reasons other than progression or death before 8 weeks will be considered evaluable for the assessment of the DCR.
 
Between 12 and 24 patients will be enrolled in the Phase I portion of the study, depending on whether DLTs occur and dose de-escalation is required. The 6 patients treated at the RP2D will be included in the Phase II portion of the study. We anticipate the combination will be well tolerated such that all of the patients in the Phase I portion are likely to be evaluable for the Phase II efficacy analysis.
 
26 evaluable patients will be enrolled in the Phase II portion of the study (though the potential drop-out rate is 10%), which will provide a 90% power to detect an improvement in the DCR from 25% (based on historical control) to 50%, assuming a 1-sided significance level of 0.1 and an accrual rate of 2 patients per month. A Simon's optimal two-stage design will be used to test the null hypothesis that the DCR $P \leq 0.25$ versus the alternative that $P > 0.5$. For the first stage, 11 patients will be entered to the study. The trial will be terminated if 2 or fewer patients achieve a PR, CR, or SD at 8 weeks. If at least 3 patients in the first stage achieve a PR, CR, or SD at 8 weeks, the trial goes on to the second stage. A total of 26 patients will be enrolled. If the total number of patients who achieve a PR, CR, or SD at 8 weeks is less than or equal to 9, the combination therapy will be rejected. If however, 10 or more patients achieve a PR, CR, or SD at 8 weeks the combination therapy will be considered for further analysis.
 
With 26 evaluable patients in the Phase II portion, combined with a minimum of 12 to a maximum of 18 patients enrolled strictly in the Phase I portion of the trial, there will be up to 44 patients enrolled. At an expected accrual rate of 3 patients per month, the expected accrual duration will be approximately 15 months.
 
Descriptive statistics will be used to summarize patients' demographics, toxicity, and quality of life. The PFS_{8weeks} will be estimated from the observed data with 95% exact binomial confidence interval. The nonparametric Kaplan-Meier method will be used to estimate the survival function and calculate the PFS and OS. The ORR will be estimated from the observed data with 95% exact binomial confidence intervals.

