performed at screening and repeated, the later procedure performed prior to dosing, will serve as a baseline for clinical assessment. A complete history and physical will be obtained at the screening visit. Additionally, labs will be reviewed/ordered during the screening visit, prior to the initiation of therapy.

Patients who pass screening will again undergo a full evaluation on Cycle 1 Day 1, including a physical examination, vital signs, performance status, chemistry, hematology, medication review, and adverse event evaluation. If any abnormality is identified at subject assessment on Cycle 1 Day 1, prior to initiating therapy, the patient will be deemed a screen failure and will not start treatment.

For patients being considered for enrollment outside of Georgetown-Lombardi, all primary source documentation should be sent to the multi-institutional coordinator and the Study Chair, [name] for review and approval. Patients must be approved for accrual prior to starting study medications. Faxed records should be sent to [contact], with an email to the multi-institutional coordinator and [name] to confirm receipt of those records.

The screening procedures include the following listed below.

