4.4.8 Imaging and Response Evaluation

Patients will undergo a baseline tumor evaluation with imaging studies within 3 weeks prior to Cycle 1 Day 1. Imaging studies should include a diagnostic CT scan of the chest, abdomen, and pelvis with PO and IV contrast (unless medically contraindicated). If a patient has an allergy to IV contrast, appropriate pre-medication can be given to prevent a contrast reaction. Patients may undergo other modalities such as an MRI instead of a CT scan at the treating physician's discretion if appropriate (such as severe allergy to CT contrast, extremity tumors, bone metastases requiring bone scans, etc.).

Response evaluation will occur every 8 weeks (regardless of treatment cycle) and at the final visit, if not performed within the last 4 weeks. Tumor response and/or disease progression will be assessed by the modality(ies) used prior to treatment. Patients will continue to remain on study as long as there is no evidence of PD and the therapy is adequately tolerated.

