9.4 Endpoints

9.4.1 Primary Endpoint

PFS at 8 weeks is a complete response (CR), partial response (PR), or stable disease (SD) by imaging study (CT or MRI), evaluated by expert radiologists using RECIST v1.1 criteria, at the 8 week response assessment. Each patient will be categorized as either success/failure for being progression free at 8 weeks.

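### Table 12 times best-response stable disease from the baseline scan, so a final-visit scan as early as day 8 or 15 after Cycle 1 Day 1 can be recorded as SD

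*Combined protocol and SAP*

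**What the plan says.** **Best response.** Sections 2.5.3 and 9.4.2.3 make best response, categorised as CR, PR or SD, a secondary endpoint. The SD row of Table 12 (section 7.3) requires that SD be "Documented at least once >4 wks. from baseline".

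**Baseline scan.** The timing is given in three ways:
- Section 4.4.8: "Patients will undergo a baseline tumor evaluation with imaging studies within 3 weeks prior to Cycle 1 Day 1".
- Section 7.2.1.3: "never more than 14 days before the beginning of the treatment".
- Section 7.1: "Assessments will be performed within 3 weeks before screening every 8 weeks thereafter".

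The screening text ahead of section 4.2.1.1 adds that, for a repeated procedure, "the later procedure performed prior to dosing, will serve as a baseline for clinical assessment".

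**Off-schedule scan.** Section 4.4.8 asks for response evaluation every 8 weeks "and at the final visit, if not performed within the last 4 weeks". Section 4.4.9.2 wants the final-visit tumour assessment done promptly after discontinuation.

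**Primary endpoint.** Section 9.4.1 counts CR, PR or SD "evaluated by expert radiologists using RECIST v1.1 criteria, at the 8 week response assessment". Section 4.4 gives that scan a window of 7 days either side. In the synopsis (Statistical Design, Feasibility, and Trial Duration), patients who meet the listed conditions "will be considered evaluable for the assessment of the DCR". One condition is that they did not leave the study before 8 weeks for a cause that is neither progression nor death.

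**The concern.** SD is meant to say that the tumour was held for a meaningful period on treatment. Under Table 12 much of the required 4 weeks can pass before the first dose. A patient who stops early for toxicity and whose final-visit scan shows neither progression nor response can then enter the best-response table as SD after little more than a week of follow-up. The primary endpoint uses the same label for status at 8 weeks. The trial would thus report SD with two very different minimum follow-up times. A reader could take the best-response SD figure, or a disease control rate built from it, as evidence of activity when part of it reflects early departure.

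**Working it through.** **1. Inputs**
- Minimum SD interval: more than 4 weeks, so at least 29 days from baseline (Table 12).
- Age of the baseline scan at Cycle 1 Day 1, *w*: up to 21 days (4.4.8), up to 14 days (7.2.1.3), or, reading 7.1 literally, up to 21 days before a screening that may itself be 21 days before dosing, 42 in all.
- Scheduled first response scan: 8 weeks ± 7 days.

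**2. Earliest day on which a scan can count as SD**

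Days elapsed since Cycle 1 Day 1 = max(0, 29 − *w*).

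| Baseline scan, days before Cycle 1 Day 1 | Earliest SD scan under Table 12, day |
|---|---|
| 42 (literal 7.1) | 0 (interval already over) |
| 21 (limit in 4.4.8) | 8 |
| 14 (limit in 7.2.1.3) | 15 |
| 7 | 22 |
| 3 | 26 |
| 0 | 29 |

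These are days from Cycle 1 Day 1 to the scan. Section 6.7.1.2 allows treatment to be held for up to 3 weeks, so actual days on drug can be fewer.

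**3. Does the plan generate such a scan?** Yes. For a patient who leaves before the 8-week assessment, the baseline scan is normally the last one. A final-visit scan is required only when that scan is more than 28 days old. Table 12 uses the same 28-day limit from the same scan, so every final-visit scan required on this ground meets the SD interval.

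**4. Comparison with the 8-week SD.** The earliest 8-week scan is day 56 − 7 = 49. The gap to the Table 12 minimum is 49 − 8 = 41 days, 49 − 15 = 34 days, or 49 − 29 = 20 days if the baseline scan is on the day of first dose. Scheduled scans (day 49 or later) always exceed 28 days from baseline, so only early off-schedule scans are in question.

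**5. Where Table 12 SD is used.** It feeds the best-response category. ORR is CR plus PR (2.2.3), so SD does not enter it. The primary count is defined separately in 9.4.1.

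**6. The plan's own design figure.** The rule is to stop at 2 or fewer of 11 and declare success at 10 or more of 26. The exact two-stage binomial gives P(success) = 0.0857 at a rate of 25% and 0.9005 at 50%, with early-stop probability 0.455 at 25%. This agrees with the stated one-sided 0.1 and 90% power. The calculation uses 8-week status only and is unchanged by Table 12.

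**7. Possible size in the best-response table.** The documents give no expected number of early toxicity leavers with a qualifying scan. As an assumption, take 1 to 3 such patients among 29 treated, the upper figure being the synopsis drop-out allowance. The SD share then rises by 1/29 = 3.4 to 3/29 = 10.3 percentage points. The upper end requires every drop-out to have been treated and to have had an early scan with neither PD nor response. In sections 4.1.2 and 9.2 the replaceable patients never start treatment, and such patients would contribute nothing.

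**The case against.** **The effect needs a particular patient.** Days 8 and 15 are the outer limits of the windows. Section 7.2.1.3 asks for baseline measurement close to the start of treatment, and a repeat pre-dose scan would become the baseline. If the baseline scan is 4 weeks old or less at the final visit, no new scan is required. This stands: such a patient *can* be recorded as SD, not *will* be. Yet even a same-day baseline leaves a minimum of day 29, still 20 days short of the earliest 8-week scan.

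**Best response and the primary endpoint are separate and may use different intervals.** True, and a shorter SD interval would be defensible if it ran from the start of treatment. The weakness is that it runs from a scan whose age at first dose varies. Section 9.5.2.1 also plans no SD-rate or disease-control analysis from Table 12, which keeps the matter small.

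**A stronger reading is tempting.** Because the synopsis words its hypothesis as DCR, a reader might infer that early leavers with Table 12 SD become successes in the go/no-go count. If 10% of patients were so counted and the rest had a 25% rate, the rate would be 0.10 + 0.90 × 0.25 = 32.5% and P(success) 0.308. The documents do not support that count. All four decision rules in that synopsis section specify SD at 8 weeks, as do 4.1.2 and 9.4.1, while 9.2 and 9.5.1 state the same rules as progression-free at 8 weeks. The synopsis also makes a patient who leaves before 8 weeks because of toxicity non-evaluable for DCR. The wording of section 2.4 is looser, but it too is tied to 8 weeks.

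**A mismatch with the historical SD rate of 25–31%** might also be inferred. The documents do not say how the cited third-line studies timed SD, so this cannot be shown.

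**Conclusion.** The defect is real but limited. Table 12 allows SD from day 8 (21-day window) or day 15 (14-day window) after Cycle 1 Day 1, and from day 22 to 29 when the baseline scan is 7 to 0 days before dosing. The final-visit rule can supply the scan. The consequence is confined to the secondary best-response SD category and any disease control rate derived from it. The primary 8-week endpoint, the stop/go rules, their error rates and ORR are unaffected, and no type I error inflation should be claimed.

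This rests on reading baseline as the pre-treatment scan, as section 7.2.3 does, and on applying section 9.4.1 and the synopsis evaluability rule as written. How many patients would be affected is not known from the documents. It is a cheap improvement, not a flaw in the decision design.

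**What to change.** - In the SD row of Table 12, replace the interval from baseline with a requirement that SD be documented at the week-8 assessment or later, meaning at least 7 weeks after Cycle 1 Day 1 given the 7-day window.
- In the best-response table, report a patient whose only non-PD scan is earlier than that as not evaluable, and keep the patient in that table's denominator.
- Reconcile the baseline-scan windows in sections 4.4.8, 7.1 and 7.2.1.3 so that one statement applies throughout.

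The synopsis decision rules need no change for this point, since they already specify 8 weeks. The cost is one table cell, one reporting sentence and a consistency edit, with no change to sample size or decision rules. All scheduled scans still qualify. The downside is that slightly fewer patients will be labelled SD.

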7.4 Definition of Disease Progression

Disease progression will be defined as:

- 1) Radiologic progression of disease by RECIST v1.1 criteria.
- 2) Clinical progression as determined by the investigator, which may be characterized as, but is not limited to:
 - a. Increase of at least 2 points in ECOG performance status attributable to cancer progression.
 - b. Requirement for palliative radiation, chemotherapy or surgery.
- 3) Death from disease progression

8.0 CORRELATIVE RESEARCH AND TUMOR BIOPSIES

8.1 Pharmacodynamic Assessment of the Efficacy of LEE011 and Everolimus

8.1.1 Introduction

The primary objective of this trial is to determine the efficacy of LEE011 and everolimus in patients with refractory mPAC. However, an important secondary endpoint is to assess the pharmacodynamic effects of the combination treatment on cell cycle, the retinoblastoma pathways and MTOR pathways, and to correlate those effects to the PFS. Thus, for all patients, we will require at least 2 serial biopsies.

- A fresh biopsy prior to treatment
- A repeat biopsy on the Cycle 1 Day 15
- An optional final biopsy after PD or off study

The first (pre-treatment) biopsy should be performed as soon as possible after consent is signed. For this reason, patients will be screened for accessibility of tumor tissue. Specifically, our radiologists will review the most recent images for each patient prior to enrollment. Only patients who, in their best estimation, have a tumor deposit(s), that are easily accessible by ultrasound or CT guidance in order to obtain serial core needle biopsies, will be eligible for study

With regards to the timing of the second biopsy, the pharmacokinetics of both LEE011 and everolimus suggest that the LEE011 reaches steady state by Day 8, and the everolimus by 2 weeks. Thus, the second biopsy was requested at a time point wherein both agents have achieved steady state, but before the week off of LEE011.

Patients will undergo core biopsies, as per standard protocol in the Department of Radiology. An 18-20 gauge needle will be used. At least four 1-2 cM core biopsies should be obtained with each biopsy. All samples should be labeled with the date, protocol number, protocol assigned patient number, and biopsy number (1 – pre-treatment; 2 – on-treatment; 3 – after PD or off study).

2 cores should be placed in screw-top tubes and frozen in liquid nitrogen.

The other 2 cores should be immediately placed in formalin and then embedded in paraffin.

Throughout the study, the following labeling procedures will be followed

